#### **6.3 Statistical Methods**

All statistical estimates (e.g., means, medians, proportions, incidence rates, mean differences, correlations, etc.) will be tabulated along with corresponding confidence intervals (CIs). To avoid overreliance on p-values, the magnitudes of estimates and the corresponding confidence intervals will be the primary focus of the analyses. Quantitative data analysis will occur using SAS or R and will be conducted under the supervision of a UNC Department of Anesthesiology biostatistician along with other members of the UNC Department of Anesthesiology research division.

We will work closely with our departmental statistician in all statistical analyses. After discussion with our biostatistician, we do plan to utilize a completely randomized study design. For our post-study analysis, we will perform analyses with and without gender stratification to assess whether gender is a contributing factor in opioid usage and pain scores.

For Aim 1 (comparing postoperative pain and anxiety scores), the following questionnaires and scales with validated scoring as above will be analyzed: short STAI, FACES, FLACC, PHBQ-AS.

For Aim 2 (comparing postoperative opioid usage), opioid usage will be converted into morphine equivalents at the time of data entry and analyzed.

For Aim 3 (assessing patient and caregiver satisfaction), qualitative satisfaction will be documented, divided into positive and negative comments. Patient satisfaction and overall experience are commonly linked to pain experienced during a hospitalization, and as a result, satisfaction with the use of VR as a method of pain control will be one of our outcomes.

We hypothesize that the use of virtual reality programs will provide superior distraction to standard of care and will result in improved pain scores and reduced opioid consumption after surgery. We will utilize two-sample t-test to compare the pain scores and opioid consumption in VR and control groups.

We will have the p-values reported and Bonferroni correction will be used to adjust for multiple comparison. P-values not reaching the significance level will be deemed as inconclusive.

If a value is missing, the measure will be negated for that participant, and we will have an incomplete data point. These incomplete data points will not be included in the analyses. This study is based on prior work by our group with a quite rare occurrence of not being able to collect all data points, given the nature of the collected data. We do not anticipate that missing values will systematically introduce any selection bias.

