## 5 STUDY EVALUATIONS AND MEASUREMENTS

- Variables that will be abstracted from the medical charts:
  - Name, medical record number, phone number
  - Age (years), gender (male or female), race or ethnicity, weight (kg), BMI (kg/m2), heart rate (0-200 beats/min), and blood pressure (0-250/0-150 mmHg) pre-operatively
  - Surgery type, current medications
  - Pain scores, vital signs
  - Intraoperative record
- o Baseline evaluation will include chart review, by phone or in person assessment for inclusion and exclusion criteria, vital sign assessment, study consent and orientation.
- Preoperatively, baseline vital signs will be obtained and recorded by nursing staff per UNC standard of care practices. Additionally, two pain scores will be assessed: FACES by the patient and FLACC by the research assistant.
- O Postoperatively, pain scores including FACES scale by the patient and FLACC scores by the research assistant will be recorded immediately prior to intervention (T=0) and at end of intervention (T=30); FLACC score will also be recorded at the 10 minute mark (T=10). PCA use, in mcg or mg as appropriate, for the hour prior to intervention (T=-60-0), during intervention (T=0-30), and one hour after intervention is complete (T=30-90) will be recorded. Total number of minutes of electronic device use will be recorded. This data will be recorded by the research assistant.
- o PCA use will be converted to morphine equivalents at time of data entry.

Descriptions of each questionnaire and scale, including total score computations:

Short State-Trait Anxiety Inventory (STAI) – 6 statements (i.e., 'I feel calm', with 1=Not at all, 2=Somewhat, 3=Moderately, 4=Very much). Scores 6-24, with 6 signifying no anxiety and 24 points signifying the highest level of anxiety. This short form of the STAI was used and validated in children aged 5-16 years (Schisler et al, 1998; Apell et al, 2011)

FACES (Wong-Baker) Pain Rating Scale – Self-assessment scale; patients select a face that illustrates the pain they are experiencing. Scores 0-10, with 0=No hurt and 10=Hurts worst (wongbakerfaces.org)

FLACC (Face, Legs, Activity, Cry, Consolability) – Observer assessment scale, with 5 categories (i.e., 'Face', with 0=No particular expression or smile, 1=Occasional grimace or frown, 2=Frequent to constant quivering chin, clenched jaw). Scores 0-2 in each category, for total scores 0-10, with 0=No observed pain and 10=Most observed pain

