PHBQ-AS (Post Hospitalization Behavior Questionnaire for Ambulatory Surgery) – 11 items on a five-point scale (i.e., 1=Much less than before, 5=Much more than before). Total scores 11-55 (Jenkins et al, 2015)

These are all validated scoring systems in pediatric populations.

We will utilize the short STAI, as above.

Units of measurement for all variables of interest: Questionnaires and scales as above. In addition, hours since anesthesia end to start of visit (hours), PCA use (mcg or mg, at T=-60-0, 0-30, 30-90 min; converted to morphine equivalents at time of data entry), patient declines (0=Yes, 1=No), total duration of electronic device use (min), presence of dizziness (0=No, 1=Yes), presence of nausea (0=No, 1=Yes), anti-nausea medication requested during intervention (0=No, 1=Yes).

Patient and caregiver satisfaction: Qualitative satisfaction will be documented, divided into positive and negative comments.

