## **6 STATISTICAL CONSIDERATIONS**

#### 6.1 Primary Outcomes

Postoperative pain scores and postoperative PCA opioid usage surrounding intervention (in morphine equivalents).

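### Opioid use, a primary outcome, is compared as an absolute amount in patients aged 11-17 without the weight already collected; if use rises with weight, this adds avoidable variance.

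*Combined protocol and SAP*

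**What the plan says.** Section 6.1 names the primary outcomes: "Postoperative pain scores and postoperative PCA opioid usage surrounding intervention (in morphine equivalents"). Section 5 gives the unit and the time windows: "PCA use (mcg or mg, at T=-60-0, 0-30, 30-90 min; converted to morphine equivalents at time of data entry"). Section 6.3 adds under Aim 2 that "opioid usage will be converted into morphine equivalents at the time of data entry and analyzed", and then gives the test: "We will utilize two-sample t-test to compare the pain scores and opioid consumption in VR and control groups".

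No section gives a per-kg unit or a weight or age covariate. Allocation takes no account of size either: "we do plan to utilize a completely randomized study design". The one patient characteristic given a role in the analysis is gender: "we will perform analyses with and without gender stratification to assess whether gender is a contributing factor in opioid usage and pain scores".

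Section 5 lists the chart variables, including "Age (years), gender (male or female), race or ethnicity, weight (kg), BMI (kg/m2"), so weight will be on file. Sections 3.1 and 3.4 set the age range at 11-17 years. Section 3.3 aims for 10 completers per arm from at most 24 enrolled. Section 6.4 says that the 20-patient pilot will be used to estimate the effect size on the primary outcome.

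**The concern.** Patients aged 11 to 17 can differ a good deal in body size. If larger patients use more opioid, part of the spread in morphine equivalents within each arm reflects size and not pain or treatment. An unadjusted t-test leaves that part in the error term, although a variable that could remove some of it is already collected.

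This matters because section 6.3 makes estimates and confidence intervals the main focus, and section 6.4 makes the effect size the pilot's product. A larger SD widens the interval, shrinks the standardized effect and carries over into the sample size of the next trial. Ten per arm leaves little precision to spare.

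**Working it through.** **The plan's own figure.** The 20 completers have no alpha, power, SD or effect size behind them, so there is no calculation to reproduce. For context, the 95% interval for a difference between two arms of 10 has half-width t(0.975, 18 df) × √(2/10) = 2.101 × 0.447 = 0.94 SD.

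**Inputs.** From the documents: 10 per arm, an absolute amount as outcome, an unadjusted t-test and no stratified allocation. Assumed, because the documents give no figures: weight CV (CVw) of 20-30%; CV of use per kg (CVr) of 40-100%; use proportional to weight, with per-kg use independent of weight.

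**Variance of the absolute amount.** With amount = weight × per-kg use,

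CV_total² = (1 + CVw²)(1 + CVr²) − 1.

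At CVw = 0.25 and CVr = 0.50: 1.0625 × 1.25 − 1 = 0.328, so CV_total = 0.573. The SD ratio to the per-kg scale is 0.573/0.50 = 1.146, and the variance ratio is 0.328/0.25 = 1.31. About 20 × 1.31 = 26 completers on the absolute scale match 20 on the per-kg scale.

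SD ratio (relative interval width) over the range:

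| Per-kg CV | Weight CV 20% | 25% | 30% |
|---|---|---|---|
| 40% | 1.14 | 1.21 | 1.29 |
| 50% | 1.10 | 1.15 | 1.20 |
| 75% | 1.05 | 1.08 | 1.12 |
| 100% | 1.04 | 1.06 | 1.09 |

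The widening therefore runs from 4% to 29%. The lower end deserves weight, because the recording windows last only 30 and 60 minutes and use over such short periods may vary widely.

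**Chance imbalance.** The difference in mean weight between the arms has relative SD CVw × √(2/10). At CVw = 0.25 this is 0.112, so a difference above 10% has a probability of about 37% (26% at CVw = 0.20, 46% at 0.30). This is the same variation as in the table, seen from another side, and must not be added to it.

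**If use is not proportional to weight.** Let use vary as weight to the power b. On the log scale the raw variance is b²σw² + σe², and the per-kg variance is (1 − b)²σw² + σe². Dividing by weight helps only when b exceeds 0.5. At b = 0 it does harm: with a weight CV of 25%, a CV of 0.50 becomes 0.57.

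**What a weight covariate does in 20 patients.** Under proportionality, a linear weight term leaves a residual variance of CVr²(1 + CVw²), which is 0.25 × 1.0625 = 0.266 at the middle values. Estimating the slope multiplies the variance by about (20 − 3)/(20 − 4) = 17/16, which gives 0.282. The t quantile rises from 2.101 to 2.110. The unadjusted interval is then √(0.328/0.282) × 2.101/2.110 = 1.07 times as wide, so the covariate recovers about half of the 15%. If use is unrelated to weight, the covariate widens the interval by about √(17/16) × 2.110/2.101 = 1.035, or 3-4%. Dividing by weight would cost about 15% in that case.

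**The case against.** The strongest objection is that the documents never say that use depends on weight. Section 3.1 says only that the surgical team orders the PCA, and no weight distribution or SD is given. That stands, and it is why the size of the effect is conditional and why the form of the fix matters. Section 6.4 does call the population homogeneous, but in contrast to all-comers in the PACU, so the remark concerns surgery and pathway and not body size.

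A reader might infer that a heavier arm would bias the comparison on top of the added variance. The documents do not support that. Allocation is completely randomized, so the comparison is unbiased in expectation, and the t-test interval already covers chance imbalance in weight.

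A reader might also infer that morphine equivalents per kg must become the primary outcome at no cost. That does not follow either. The table takes the case of exact proportionality, and division adds noise when b is below 0.5.

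Two other features of the plan could absorb part of a size effect. The pre-session window (T=-60-0) reflects each patient's own level of use and would leave less for weight to explain, but the plan does not say that it enters the comparison. The gender-stratified analysis would capture size only in part, and its stated purpose is to examine gender.

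**Conclusion.** The point holds as a matter of precision. An absolute amount is compared without adjustment while a plausible predictor of it, already on file, goes unused. Under proportionality and the assumed CVs, the interval is about 4-29% wider than on a per-kg scale. At CVs of 50% and 25% it is about 15% wider. The matching variance factor of 1.31 means 31% more patients for the same precision, or 1 − 1/1.31 = 24% of the information lost; 31% should not be read as the loss. The gain shrinks if the pre-session window is also used, and disappears if use does not rise with weight.

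Nothing here invalidates the plan. The raw comparison is valid, and per-kg results could still be derived later because weight is kept. The reason to settle the matter beforehand is that choosing the scale after seeing the data allows selective reporting.

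**What to change.** In section 6.3, Aim 2, state before any data are examined that the opioid comparison accounts for preoperative weight. The preferred form is a linear model with arm and weight as terms, plus the T=-60-0 window if it is adopted as a baseline. This does not assume proportionality. Report morphine equivalents per kg and the raw amount alongside, each with its SD and confidence interval, so that the next trial can choose its scale from data.

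The cost is one model term, with no new data and no extra visits. In a 20-patient analysis it uses one degree of freedom, and it widens the interval by about 3-4% if weight turns out to be unrelated to use. It is a cheap improvement, though not an entirely free one.

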Both iPads and VR devices are interactive (regardless of fingers versus head movement) and this type of movement difference should not confound results. Our study aims to assess whether the VR immersive experience provides superior distraction to the standard of care (iPad use), thus by nature of the study design we are studying the difference in the two distinct types of experiences. Finger versus head movement use is inherent to the types of distraction and central to the distinct experiences. Similarly, there will be different apps between VR and iPad platforms by nature of the differences in platforms. Our goal is to examine whether an immersive experience is more beneficial than an iPad-based experience, rather than examine specific styles of games.

There will be no restriction to personal electronic use. Both groups will have access to their personal devices (cell phones, iPads) as is the standard of care. The study iPad will only be offered at specific times as designated twice a day on POD#1 for participants in the control group. Outside of the study windows, participants will not be provided with hospital iPads. Personal electronic devices including iPads are acceptable, as is the standard of care for patients to bring whatever they see fit into the hospital.

There will be a variety of popular games and apps, deemed to be content- and age-appropriate by the Child Life specialists. Program offerings will not vary by specific age or gender; our study will only include ages 11-17 and per discussion with Child Life the programs do not need to be subdivided to remain appropriate within this age range.

Standard of care for both groups will include PCA use as ordered by the surgical team as well as routine Child Life visits. The Child Life team is an integral part of pediatric postoperative recovery at UNC.

The following will be recorded: Number of hours since anesthesia end. Pain scores including FACES scale by the patient and FLACC scores by the research assistant will be recorded immediately prior to intervention (T=0) and at end of intervention (T=30); FLACC score will also be recorded at the 10 minute mark (T=10). PCA use, in mcg or mg as appropriate, for the hour prior to intervention (T=-60-0), during intervention (T=0-30), and one hour after intervention is complete (T=30-90) will be recorded. Total number of minutes of electronic device use will be recorded. PCA use will be converted to morphine equivalents at time of data entry.

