## 4.2 Intervention/Treatment procedures (by visits)

There will be two intervention/treatment visits, both occurring on POD#1. On POD#1 in the morning, patients in both groups will be visited by the research assistant. Patients in the VR arm will be offered the VR device for up to 30 minutes. Patients in the control arm will be offered an iPad for up to 30 minutes. After a total of 30 minutes maximum, the session will end. Routine data will be collected on pain scores and PCA use as above for both groups. On POD #1 in the afternoon, a research assistant will return for patients in both groups. For participants in the intervention group, this VR session will be again offered for up to 30 minutes. Patients in the control arm will be offered an iPad for up to 30 minutes. If a patient declines to participate, the reason for declining will be asked for and recorded.

To evaluate efficacy, the following will be recorded:

- Primary outcomes:
  - Postoperative pain scores
  - Postoperative PCA opioid use surrounding intervention (morphine equivalents)
- Secondary outcomes:
  - Patient and caregiver satisfaction scores
  - Presence of dizziness/nausea
  - Time of discontinuation of VR if less than 30 minutes

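### Section 6.3 names only a two-sample t-test and gives the pre-session pain score (T=0) and pre-session PCA use (T=-60-0) no role, which costs precision if they correlate moderately with the outcome and leaves the opioid outcome open to more than one reading

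*Combined protocol and SAP*

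**What the plan says.** Section 6.3 of the combined protocol and SAP names one between-arm method for the primary outcomes: "We will utilize two-sample t-test to compare the pain scores and opioid consumption in VR and control groups". It adds a Bonferroni correction and, for gender, "we will perform analyses with and without gender stratification". Neither gives pre-session values a role. Section 5.1 says only that scores and PCA usage will be compared between arms.

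The pre-session data exist. Under the study phases in section 3.1, pain scores "will be recorded immediately prior to intervention (T=0) and at end of intervention (T=30", and PCA use "for the hour prior to intervention (T=-60-0), during intervention (T=0-30), and one hour after intervention is complete (T=30-90) will be recorded". Section 4.2 provides two sessions on POD#1.

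Section 6.1 defines the primary outcomes as "Postoperative pain scores and postoperative PCA opioid usage surrounding intervention (in morphine equivalents"; section 4.2 lists "Postoperative PCA opioid use surrounding intervention (morphine equivalents". Neither says which recorded windows count.

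Section 6.3 also states that "the magnitudes of estimates and the corresponding confidence intervals will be the primary focus of the analyses", and section 6.4 says the pilot (N=20) will be used to estimate the effect size.

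**The concern.** The pilot's main statistical product is an effect estimate with a CI. With about 20 patients, CI width decides how useful that estimate is for planning a later trial, and a covariate that costs nothing to collect has no stated use.

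For pain, the t-test could be run on the post-session value or on the change from T=0. For opioid use there is a third reading: the recorded windows run from -60 to 90 minutes, so the definition could put the pre-session hour inside the outcome. That hour cannot be affected by the session that follows it. The readings give different estimates or CI widths from the same patients, so the choice should be fixed before the data are seen.

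**Working it through.** **Inputs.** 10 completed patients per arm (sections 3.3 and 4.7). The documents give no SD, no pre/post correlation r and no numerical significance level, and N = 20 rests on no power calculation, so there is no plan figure to reproduce. Assumptions: two-sided 95% CI, roughly normal and linear data, the same r in both arms. Half-widths are in SDs of the post-session value.

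**1. t-test on the post-session value.** t(0.975, 18) × √(2/10) = 2.1009 × 0.4472 = 0.940, whatever r is.

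**2. ANCOVA with one covariate.** Half-width = t(0.975, N−3) × √(1/n1 + 1/n2) × √(1−r²) × √(1 + 1/(N−4)). The last factor is the average cost of chance covariate imbalance. For 10 and 10, with t(0.975, 17) = 2.1098: 2.1098 × 0.4472 × √1.0625 × √(1−r²) = 0.973 × √(1−r²).

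| r | ANCOVA | t-test on post value | ratio |
|---|---|---|---|
| 0 | 0.973 | 0.940 | 1.035 |
| 0.3 | 0.928 | 0.940 | 0.987 |
| 0.5 | 0.842 | 0.940 | 0.896 |
| 0.7 | 0.695 | 0.940 | 0.739 |

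The ANCOVA widths at r = 0.3, 0.5 and 0.7 are those of a t-test with about 10, 12 and 17 per arm.

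**3. Break-even against the post-value t-test.** r = √(1 − (0.940/0.973)²) = 0.258 with unrounded inputs. If patients lacking only the baseline drop out of the adjusted model, break-even against the t-test on all 20 rises to 0.357 (9 and 10) and 0.429 (9 and 9). For confidence levels from 90% to 99.375%, the 10-and-10 threshold stays at 0.25 to 0.27.

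**4. These are averages.** In 40,000 simulated trials per setting, ANCOVA gave the narrower CI in 42%, 48%, 64%, 80% and 97% of trials at r = 0.26, 0.3, 0.4, 0.5 and 0.7.

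**5. Change-score t-test, equal pre and post SDs.** Half-width = 0.940 × √(2−2r): 1.11, 0.94 and 0.73 at r = 0.3, 0.5 and 0.7. Setting this equal to ANCOVA gives r = 2/1.0715 − 1 = 0.867, where 1.0715 is the squared ratio at r = 0.

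**6. Change score, unequal SDs.** With k = pre SD / post-start SD, half-width = 0.940 × √(1 + k² − 2rk). For PCA use, the pre-session window is 60 minutes and the post-start windows total 90, so k = 2/3 is a working assumption.

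| r | change score, k = 2/3 | ANCOVA |
|---|---|---|
| 0.3 | 0.960 | 0.928 |
| 0.5 | 0.829 | 0.842 |
| 0.6 | 0.754 | 0.778 |
| 0.7 | 0.672 | 0.695 |

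Here the change score is narrower for r of about 0.42 to 0.82; with k = 0.5, for r of about 0.24 to 0.69. Its advantage is at most about 3.5%. The ANCOVA width does not depend on k.

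**7. Opioid total with the pre-session hour included.** 60 of 150 recorded minutes (40%) precede the device. Half-width = 0.940 × √(1 + k² + 2rk) = 1.28, 1.37 and 1.45 at r = 0.3, 0.5 and 0.7 with k = 2/3. For k from 0.5 to 1 the ranges are 1.17–1.52, 1.24–1.63 and 1.31–1.73.

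**8. Bounded and skewed data (all inputs assumed).** Simulated FACES scores (0, 2, …, 10; mean 4, SD 2.5) gave ANCOVA coverage of 94.8–95.1%. Simulated PCA dose counts with zeros gave 95.2–95.5%.

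**The case against.** The strongest reply is that the t-test is valid under randomization, that its CI already allows for chance imbalance, and that r is unknown. In a pilot, replacing a valid test on an unknown r can look like preference: near r = 0.3 ANCOVA wins in only about half of single trials, and at r = 0 it widens the CI. The validity point stands, and nothing here says the t-test is biased. But the possible loss is small and bounded, the possible gain is not small, and the plan itself puts estimates and CIs first.

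A second reply is that section 6.1 fixes no scale, time point or session, so the real gap is endpoint definition. That is partly right: stating the role of T=-60-0 resolves the opioid ambiguity under any test. It does not remove the precision point, because a same-scale baseline covariate can be specified for whichever endpoint the sponsor chooses.

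A reader might infer that ANCOVA beats a change score for both outcomes whenever r is below about 0.87. That needs equal pre and post SDs, and the documents give no SDs. For pain it is a reasonable working assumption because the scale is the same at both times, though a post SD 1.1 times the pre SD would already make the change score narrower for r of about 0.73 to 0.97. For PCA use the window lengths differ and step 6 shows the opposite direction over a wide range of r. A reader might also infer that the plan does count the pre-session hour in the opioid outcome. The wording permits that reading but does not state it.

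**Conclusion.** The point holds as a matter of precision and, for opioid use, of which quantity is estimated. The plan collects T=0 pain and T=-60-0 PCA use in both arms and gives them no analytic role. Relative to a t-test on the post-session value, ANCOVA gains almost nothing near r = 0.3, about 10% in CI width at r = 0.5 and about 26% at r = 0.7 (1 − 0.739). It loses up to about 3.5% if r is near 0. Relative to a change score the 0.87 threshold is for equal SDs only; for PCA use a raw change score may be slightly narrower, by no more than about 3.5%. Counting the pre-session hour in the opioid outcome gives the widest interval in every case shown.

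The figures rest on 10 per arm, a 95% CI and roughly normal, linear data. Because r is not in the documents, they show when adjustment helps, not that it will. The change is worth making, but its absence does not invalidate the planned analysis.

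**What to change.** - **Section 6.1:** state that T=-60-0 PCA use is a baseline and not part of the opioid outcome.
- **Section 6.3:** make the primary comparison for each primary outcome an ANCOVA of the post-start value on arm with one prespecified covariate: the same scale's T=0 score for pain, and T=-60-0 morphine equivalents for PCA use. The sponsor chooses the scale, time point and session.
- **Afternoon session:** use the morning pre-session value as covariate, because the afternoon T=0 follows the first device exposure. Expect a smaller gain there; it was not quantified.
- **Reporting:** give the adjusted difference with its CI and keep the unadjusted t-test as a sensitivity analysis, which also retains patients who lack only the baseline. The plan already says that "mean differences, correlations, etc.) will be tabulated along with corresponding confidence intervals"; name the pre/post correlation among them. Tabulate the morning pre-session values by arm, since they follow randomization and device orientation.

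**Cost.** Wording only; all variables are already collected. One degree of freedom per model, a CI up to about 3.5% wider on average if r is near 0, and no guarantee of narrowing in a single trial. Under the missing-value rule in section 6.3, a patient missing only the baseline leaves the adjusted model (break-even r about 0.36 if one is lost, 0.43 if two); that section expects missing values to be rare.

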## 2 STUDY OBJECTIVES

The purpose of this study is to determine whether the use of virtual reality after pediatric idiopathic scoliosis surgery influences pain perception. We hypothesize that the use of virtual reality programs will provide superior distraction to standard electronic use and will result in improved pain scores and reduced opioid consumption after surgery.

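### Holm's step-down could replace Bonferroni in section 6.3 at the same familywise error bound; Bonferroni is valid, and the gain is confined to second and later rejections

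*Combined protocol and SAP*

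**What the plan says.** Section 6.3 (Statistical Methods) names the test: "We will utilize two-sample t-test to compare the pain scores and opioid consumption in VR and control groups". It then sets the multiplicity rule: "We will have the p-values reported and Bonferroni correction will be used to adjust for multiple comparison". A result that misses the adjusted level gets a fixed label: "P-values not reaching the significance level will be deemed as inconclusive". No step-down or other sequential procedure is mentioned. No alpha, number of comparisons or list of tests in the family is given.

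The hypothesis in section 2 has two parts, namely that virtual reality "will result in improved pain scores and reduced opioid consumption after surgery". Section 6.1 makes both parts primary: "Postoperative pain scores and postoperative PCA opioid usage surrounding intervention (in morphine equivalents". The plan does not say whether success needs one part or both.

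Two further statements bear on the weight of the point. Section 6.3 puts estimates and confidence intervals ahead of p-values. Section 6.4 describes a pilot of 20 completed patients with an unknown effect size and claims no power.

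**The concern.** Bonferroni judges every outcome in a family of m tests at alpha/m, even after another outcome has already been shown. Holm judges the smallest p-value at alpha/m, the next at alpha/(m−1), and so on, stopping at the first failure. It controls familywise error at the same level whatever the correlation between outcomes, and it rejects everything Bonferroni rejects and sometimes more.

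This matters here because the hypothesis joins pain and opioid use and the plan labels each test result. With 10 completed patients per arm, a second outcome that could be declared at a fully controlled error rate would be called inconclusive under the rule as written.

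**Working it through.** **No figure to reproduce.** The sample size in section 6.4 does not rest on alpha, power, an effect size or an SD, so no stated number depends on the choice of correction.

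**Inputs from the documents.** Target of 10 completed per arm (section 3.3); two-sample t-test for each outcome and Bonferroni (section 6.3); two primary constructs (section 6.1).

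**Assumptions.** Two-sided familywise alpha 0.05; m=2; normal outcomes; standardised effect d from 0.5 to 1.5, equal for both outcomes unless stated; correlation r between outcomes of 0, 0.3 or 0.6.

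**The two rules for m=2**, with ordered p-values p(1) ≤ p(2):
- Bonferroni rejects each p ≤ 0.05/2 = 0.025. Adjusted p-values are 2p(1) and 2p(2), capped at 1.
- Holm rejects p(1) if p(1) ≤ 0.025 and, only then, p(2) if p(2) ≤ 0.05. Adjusted p-values are 2p(1) and max(2p(1), p(2)), capped at 1.

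The decisions differ only when p(1) ≤ 0.025 and 0.025 < p(2) ≤ 0.05. The first rejection uses the same cut-off under both rules, so the chance of at least one rejection cannot change.

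**Power per test** (exact noncentral t, 10 per arm, 0.025 two-sided): 11.6% at d=0.5, 28.2% at d=0.8, 43.6% at d=1.0, 60.0% at d=1.2, 80.9% at d=1.5. The effect detectable with 80% power is d=1.48 at 0.025 and d=1.33 at an unadjusted 0.05.

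**Simulation**, 100,000 trials per setting. The Monte Carlo standard error is at most √(0.5×0.5/100,000) = 0.16 points.

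| d (both outcomes) | At least one, either rule, r=0.3 | Both, Bonferroni → Holm, r=0.3 | Both, Bonferroni → Holm, r=0 | Both, Bonferroni → Holm, r=0.6 |
|---|---|---|---|---|
| 0.5 | 20.6% | 2.5% → 4.8% | 1.3% → 2.9% | 4.4% → 7.7% |
| 0.8 | 45.3% | 11.4% → 18.5% | 7.9% → 14.3% | 15.4% → 23.3% |
| 1.0 | 64.1% | 23.4% → 34.4% | 19.1% → 30.2% | 28.3% → 39.1% |
| 1.2 | 79.7% | 40.1% → 53.2% | 36.0% → 50.0% | 45.2% → 57.3% |
| 1.5 | 94.0% | 67.6% → 79.0% | 65.3% → 77.9% | 70.7% → 80.7% |

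Consistency check: with two outcomes, average power = (at least one + both)/2. At d=0.8, r=0.3, Bonferroni gives (45.3+11.4)/2 = 28.4%, against 28.2% exact. Holm gives (45.3+18.5)/2 = 31.9%. The gain in average power is thus half the gain for both.

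**Only one outcome with an effect** (r=0.3): its power goes from 28.1% to 28.4% at d=0.8, and from 59.9% to 60.2% at d=1.2.

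**Error rates.** With no effect on either outcome, familywise error is the same under both rules (4.5% to 5.0%). With one true effect of 0.8 or 1.2, the false rejection rate for the other outcome is about 2.5% under Bonferroni and 3.2% to 4.0% under Holm. Holm uses more of the allowance but stays within 5%.

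**Larger families.** The plan does not fix m=2. FACES at T=30 and FLACC at T=10 and T=30 are 3 scores, or 6 over two sessions. The PCA windows from T=0 onward are 2, or 4 over two sessions. That could be 6+4 = 10 tests at 0.05/10 = 0.005 each, before any gender analyses. With m=8, d=0.8 and r=0.3, average power goes from 13.1% to 15.4%, and the chance of at least one rejection is 54.9% under both rules. At d=1.2 average power goes from 37.1% to 47.2%.

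**The case against.** The strongest reply is that nothing here is wrong. Bonferroni controls familywise error, the trial is a pilot with no power target, and a missed result is called inconclusive rather than negative. All of that stands. A reader might infer that the correction makes the planned analysis invalid, or that it lowers the chance of any positive finding. The documents and the arithmetic support neither. Sample size is the main limit on power: even without adjustment, 80% power needs d=1.33.

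Second, the plan puts confidence intervals first. Bonferroni has simple matching simultaneous intervals (97.5% each for m=2), and Holm does not. An outcome with p between 0.025 and 0.05 could be significant under Holm while its 97.5% interval includes zero. This is a real but small cost, because section 6.3 attaches the correction to the p-values and does not describe the intervals as adjusted.

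Third, a reader might take the two-part hypothesis to mean that both outcomes must succeed. If so, each could be tested at full alpha with no correction. At d=0.8 and r=0.3 that gives 19.9% for both, against 18.5% with Holm and 11.4% with Bonferroni. The plan does not state such a rule and does specify a correction. Given that choice, Holm recovers most of the difference.

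Fourth, neither method can be run until the family and alpha are fixed. That is the larger gap. It lowers the priority of this point but does not remove it, since Holm never rejects less for any family.

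**Conclusion.** The point holds as an optional improvement. For test decisions, Holm is never worse than the planned rule at the same familywise bound, and the benefit lies wholly in second and later rejections. For two outcomes with equal effects and r=0.3, the chance of showing both rises by 2.3 points at d=0.5 (4.8−2.5), 7.1 at d=0.8 (18.5−11.4), 11.0 at d=1.0 (34.4−23.4) and 11.4 at d=1.5 (79.0−67.6). Over r=0 to 0.6 the gain runs from 1.6 points (2.9−1.3, d=0.5, r=0) to 14.0 points (50.0−36.0, d=1.2, r=0). It is negligible if only one outcome responds.

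These sizes rest on assumed values for alpha, m, d and r, none of which the plan gives. They also assume normal outcomes and 10 completed per arm. The ordering of the two rules depends on none of these assumptions. No figure stated in the plan changes.

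**What to change.** In section 6.3, replace the Bonferroni correction with the Holm step-down method and report Holm-adjusted p-values. In the same edit, list the tests that form the family and state the two-sided familywise alpha. For a family of two at 0.05, the smaller p-value is judged at 0.025 and, if it passes, the other at 0.05.

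Keep estimates and confidence intervals as the primary focus, reported as planned, and say whether they are adjusted for multiplicity. If Bonferroni-level intervals are shown, add a note that they need not agree with a Holm decision.

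The cost of the change of method is one phrase in the plan and one standard option in SAS or R. Patients, data collection and sample size are unaffected. The price is the loss of simple simultaneous intervals that match the tests.
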